## (9) DATA ANALYSIS/METHODS:

### ***Data Storage.***

The personal demographic data for each participant will be blinded from the researchers, and a coded identification number will be used to track all collected data. Data will be stored on password-protected computers and only pertinent research personnel will have access. Data forms will be stored by coded identification number in a locked cabinet to which only pertinent research personnel have access. All data will be collected for research purposes only.

### ***Data Analysis.***

Data processing and analysis will be performed using a series of existing software including FSL (FMRIB's Diffusion Toolbox in FSL Software, Oxford, UK), AFNI (Cox, 1996), SPM (Statistical Parametric Mapping analysis package, Wellcome Department of Cognitive Neurology, London, UK), DTIStudio (John Hopkins University, Baltimore, MD; Jiang et al., 2006), as well as additional customized software written in Matlab or IDL.

DTI data will first be subjected to preprocessing to correct for Eddy current and head motion artifact, followed by calculation of the three diffusion eigenvectors and eigenvalues. DTI measures, including fractional anisotropy (FA), mean diffusivity (MD), axial diffusivity (AD), and radial diffusivity (RD) will be calculated. The regions of interest will be manually determined in major white matter areas such as corpus callosum, internal capsule, and external capsule. After being normalized to a common template, voxel based group analysis can be performed to explore brain regions that present significant group difference or longitudinal changes. Fiber tracking can be performed to generate white matter tracts in different areas in the brain, e.g., cortico-spinal tract, different segments in corpus callosum, optic radiation, cingulum superior longitudinal fasciculus, and others.

Functional fMRI (resting state fMRI) will also be subjected to routine image pre-processing pipeline. Functional connectivity analysis will be performed, using the CONN toolbox, <http://www.nitrc.org/projects/conn/>) between all brain regions that are involved in the proper functioning of default mode network, sensory motor network, visual network, and a series of other networks that are known to be strongly functionally connected during resting state. SWI, HARDI and ASL BOLD will undergo standard image post-processing.

***Statistical considerations.*** The data analysis will begin with a review of descriptive statistics for all major variables and all major subgroupings of variables in the data set. For the inferential methods, we will use a number of different generalized linear modeling techniques, including linear regression models. All analyses will be conducted using SAS® version 9.3 (SAS Inst, Cary, NC), or Mplus (Muthén, 2007). Initial analyses will be undertaken to inspect data for errors, inconsistencies, and incomplete information. This will include examining the data with simple frequency tables and dot plots for univariate data and scatter plots and multi-way dot plots for bivariate and multivariate data. Data anomalies that cannot be resolved by the Biostatistical/data management team will be sent as queries via

email to the project investigator for clarification and/or correction. During the verification process, outlying values will be corrected if necessary. Incomplete information will be corrected and the project investigator will receive updates. To summarize bivariate relationships among predictors and between predictors and outcomes, Chi-square of Fisher's exact test or Spearman's rank correlation coefficient, will be used, as appropriate. For reporting inferential statistics, such as differences in rates or means, 95 percent confidence intervals will be used extensively to quantify degree of clinical efficacy. Unless otherwise stated, statistical tests are considered two-sided and a .05 significance level is used. All models will be adjusted for potential independent predictor variables but will be limited to the number of predictors we can fit in a regression model while maintaining a valid and reliable model. Candidate predictors include amount of playing time, amount of practice time, previous mTBI, weight, age and height. Collinearity will be examined. Linearity assumptions will be checked and transformations examined. In those cases, a log transformation, polynomial terms, or restricted cubic splines will likely be used to relax the assumption of linearity in the regression models. We will remove the nonlinear terms or transformation only if the nonlinear test is non-significant with a  $p \geq .10$ . Additionally, overly-influential observations and distributional assumptions will be checked. Models will be interpreted graphically, predicted values will be examined, and appropriate significance tests will be utilized.

***Statistical analyses.*** - Statistical analysis of outcomes measures will be done using SAS®, version 9.3 (SAS Institute, Cary, NC) and SPSS statistical software (SPSS Inc, Chicago IL). Comparisons between the testing conditions (collar vs. no collar) will be made using Analysis of Covariance, in order to control for time (pre vs post season) and condition (collar versus no collar). We will also conduct correlation analysis to test the association between imaging biomarkers (as described above) with the results obtained from the impact surveillance. The collision indices, including total number of collisions, number of collisions from front, back, left, right, top, bottom, G force, and timing of each collision will all be recorded and tested in the analysis. Secondary analysis to compare the intervention with no intervention and calculate the rates would involve a Poisson model, using an offset to account for the playing time and exposure to concussive impact for each of the study participants. We will calculate the rate and the associated 95% confidence interval. SAS®, PROC GENMOD will be used for analysis, which allows us to account for the fixed and random effects, use the appropriate link function, and the offset for amount of playing time exposure.

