**(1) ABSTRACT:**

Significant morbidity, mortality, and related costs are caused by traumatic brain injury (TBI). A simple, effective, and lightweight device worn by athletes or war fighters in the field, designed to mitigate TBI resulting from blast trauma or concussive events, would save lives, and the huge costs incurred for life-treatment of surviving victims. An externally-worn medical device (the Device) that applies mild jugular vein compression according to the principle of the Queckenstedt Maneuver, is being developed by Q30 Sports Science, LLC (Q30). Preliminary research suggests that the Device has the potential to reduce the likelihood of TBI. The currently developed collar (Smith 2009, Smith and Fisher 2011, Smith and Fisher 2011, Smith 2012) has been approved for studies in humans (IRB 2013-2240) and the results indicate safety for use during high demand and maximal exertion activities. Regarding safety, the externally worn collar is meticulously designed to mimic the body's own omohyoid muscle actions upon the jugular veins that will provide similar pressure and volume increases not to surpass that of a yawn or the mere act of just lying down.

This study will investigate the effectiveness of this device in high school athletes playing a non-helmeted sport such as soccer. Athletes participating in this study will be randomly assigned to one of two groups: 1) Device wearing during the season or 2) Non-device wearing during the season. This study will focus on the use and effectiveness of the device solely in females, as male football and hockey players have previously been investigated. All participants will be outfitted with an adhesive patch-like accelerometer (which will be placed behind the ear (*Xpatch-X2 Biosystems* [http://www.x2biosystems.com/x2\\_x\\_patch/](http://www.x2biosystems.com/x2_x_patch/)) which will measure the magnitude of every impact to the head sustained by the athlete. Effectiveness of the device will be determined via differences in longitudinal brain imaging and functional testing following competitive soccer participation. A subset of athletes who report a diagnosed concussion will also receive additional brain neuroanatomical and neurophysiological testing within a week following the diagnosed concussive event. At each of these time points participants will also undergo various neurocognitive assessments outlined below.

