diffusion tensor imaging (DTI), Based on pre-clinical data we hypothesized that collar imparted jugular compression that minimally restricts venous outflow to encourage cerebral venous sinus engorgement would reduce brain injury biomarkers in athletes exposed to head impacts during a competitive football season. This project utilized a prospective controlled trial to evaluate effects of mild jugular vein (i.e., neck) compression (collar; n=31) relative to controls (no-collar; n=30) during a competitive football season (males;  $17.04 \pm 0.67$  years). Helmet sensors were used to collect daily impact data in excess of 20 g (games and practices) and the primary outcome measures, which included changes in white matter microstructure, were assessed by diffusion tensor imaging (DTI). Specifically, four DTI measures including fractional anisotropy (FA), mean diffusivity (MD), axial diffusivity (AD), and radial diffusivity (RD) were analyzed using a Tract-Based Spatial Statistics (TBSS) approach—a voxel based analysis. The final analyses included both an intent to treat (ITT) and per protocol evaluation of the collar intervention. The ITT analysis indicated a consistent vascular response by the athletes to collar compression, as indicated by internal jugular vein dilation (IJV) superior to its application ( $p < .01$ ). Both groups experienced similar overall g-forces and total head impacts during the competitive football season (impacts  $> 20$  g; collar 16983 vs no-collar 17750 ( $p > .05$ )). Significant pre- to post-season reduction in MD, AD, and RD (corrected  $p < .05$ ) was evidenced by extensive WM areas in the no-collar group, while no statistically significant longitudinal change was indicated for any of the DTI measures in any WM region in the collar group. Comparing the two groups, the no-collar group demonstrated significantly larger pre- to post-season DTI change in many WM regions (corrected  $p < .05$ ). Correlation analysis also showed initial evidence of significant correlation between the change in AD in some WM regions and the number of impacts and/or the cumulative G-force experienced in the no-collar group (all  $p < .05$ ). Per protocol, results were consistent with presented ITT findings with an expected increase in effect sizes noted in most voxel analyses. Our findings, based on four DTI measures known to relate to brain injury, indicate a consistent reduction of change in diffusivity parameters noted in the no-collar group at post-season. This is a literature driven sign of sub-threshold white matter injury due to repetitive head impacts during the competitive season. The smaller and statistically non-significant change in diffusivity in the collar group evidences a protective effect from the induced jugular outflow impedance. Restated, the approach to impede IVJ blood flow appears to have ameliorated the detrimental effects that resulted from a season of head impacts. The current study presents the first football related prospective longitudinal data and demonstrates a novel, in vivo, approach to protect the brain from football related head impacts. These results build on prior research and evidence the need for future work to determine if this novel method for brain injury prevention is both safe and effective.

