
#### (4) STUDY DESIGN:

The current project will be designed following a prospective longitudinal study design. All MRI scanning will be performed on a 3 Tesla Philips Achieva MRI scanner located in Imaging Research Center (IRC) in the Cincinnati Children's Hospital Research Foundation (CCHRf). Sedation will not be used for any of the test visits. The entire MRI series, including anatomical imaging, DTI, resting state fMRI, SWI, HARDI, ASL and BOLD will be completed in 60 minutes or less (see Table 1 for detailed specifications). Peripheral pulse oximetry and respiration waveforms will be collected for signal correction in functional MRI in order to improve data analysis for resting state fmri to minimize the potential confounding

effect from the physiological changes. All functional and neurocognitive testing will be performed at the Cincinnati Children’s Hospital Human Performance Laboratory.

**Table 1.** Image sequence, mode and analysis. Imaging will be completed in 60 minutes or less.

Sequence	Resolution	Mode	Analysis	Time (min)
3D T1	1x1x1 mm	Anatomy	Visual /Volumetrics/registration	5
DTI	2x2x2 mm	WM microstructure	Visual/ROI/TBSS/structural connectivity	12
rs-fMRI	3x3x4 mm	Network Connectivity	Functional connectivity	10
N-back fMRI	3x3x4 mm	BOLD activation	Quantitative	6
HARDI	2x2x2 mm	WM microstructure	Tractography, structural connectivity	12
SWI	SWI	Hemorrhagic Injury	Visual examination for incidental finding	6
			Total Time	~57 min

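### DTI regions of interest are set by hand in a device versus no-device trial, and no masking of the image reader to arm or visit is described

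*Combined protocol and SAP*

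**What the plan says.** Section 9 (Data Analysis) sets out the diffusion measures, "DTI measures, including fractional anisotropy (FA), mean diffusivity (MD), axial diffusivity (AD), and radial diffusivity (RD) will be calculated", and then how regions are obtained: "The regions of interest will be manually determined in major white matter areas such as corpus callosum, internal capsule, and external capsule". It gives no reader instructions, number of readers, repeatability check or masking.

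The same paragraph names a template-based route, worded as optional: "After being normalized to a common template, voxel based group analysis can be performed". In Section 4, Table 1 lists the DTI analyses as "Visual/ROI/TBSS/structural connectivity". Under Summary of Prior Work (Section 3), the DTI measures of the earlier football trial "were analyzed using a Tract-Based Spatial Statistics (TBSS) approach—a voxel based analysis".

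The groups in the Abstract are "1) Device wearing during the season or 2) Non-device wearing during the season". The Abstract rests effectiveness on longitudinal imaging and functional testing together. Section 8 (Injury Surveillance) has the study coordinator supply each team with its assigned condition and track each athlete's use.

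The only blinding statement is in Section 9 (Data Storage): "The personal demographic data for each participant will be blinded from the researchers", alongside a coded identification number. Section 15 repeats the coded number as a privacy safeguard.

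**The concern.** Placing a region by hand is a matter of judgement. Small differences in where a boundary falls alter the mean FA, MD, AD or RD inside it. If the person drawing knows which athletes wore the collar, expectation can enter the measurement, and a larger sample does not remove that kind of error.

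The expectation is present in the protocol itself. Summary of Prior Work reports diffusion changes in unprotected hockey and football athletes and no significant change in those wearing the collar, and it interprets the football result as protection. The design offers no barrier of its own, because there is no sham collar. What is at stake is whether a difference in region-based DTI measures can be read as an effect of the device.

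**Working it through.** **1. Is a subjective step specified?** Yes. Manual determination is stated with *will*. Voxel-based analysis and fibre tracking are stated with *can*.

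**2. Is the reader masked to arm or visit?** The statements that come closest are the blinding of demographic data (Section 9, Data Storage) and the coded identification number (Sections 9 and 15). Neither mentions arm or visit. A code that stays with a participant can be linked to her arm, and it does not distinguish or conceal the two scan dates.

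**3. Which knowledge affects which comparison?** Let the reader's shift in measured pre-to-post change be s_D in the device arm and s_C in the control arm. The bias in the between-arm contrast is b = s_D − s_C.
- Visit known, arm unknown: s_D = s_C, so b = 0. The shift remains in each within-arm change.
- Arm known: s_D and s_C can differ, so b can be non-zero.

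The two kinds of masking therefore protect different claims. Section 9 needs both, because it plans a collar versus no-collar comparison and also looks for longitudinal change.

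**4. How large could the effect be?** The plan gives no power calculation, effect size, SD, allocation ratio or dropout rate, so there is no stated figure to reproduce. What follows is an illustration.

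Inputs:
- Two-sided 0.05 level: Section 9, Statistical considerations.
- Recruitment ceiling of 150: Section 6.
- Equal split, no loss and independent athletes (75 per arm): assumed.
- Lower case of 50 per arm, as if a third had no usable pair of scans: assumed. Section 8 does allow athletes with MRI contraindications to skip imaging.
- b = 0.1, 0.2 or 0.3 SD of the outcome: assumed, with no anchor in the document.

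Formulas, for n per arm: SE = √(2/n) SD. Error rate = P(|Z + b/SE| > 1.96), with Z standard normal.

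SE = √(2/75) = 0.163 SD for 75 per arm, and √(2/50) = 0.200 SD for 50 per arm.

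| b (SD) | b/SE, 75 per arm | Error rate | b/SE, 50 per arm | Error rate |
|---|---|---|---|---|
| 0 | 0 | 5.0% | 0 | 5.0% |
| 0.1 | 0.612 | 9.4% | 0.500 | 7.9% |
| 0.2 | 1.225 | 23.2% | 1.000 | 17.0% |
| 0.3 | 1.837 | 45.1% | 1.500 | 32.3% |

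For scale, the difference detectable with 80% power at 75 per arm is (1.960 + 0.842) × 0.163 = 0.46 SD. A bias of 0.1 to 0.2 SD is about 22% to 44% of that.

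**5. After the change.** With regions fixed on the template, or with reading masked to arm, the arm-related placement bias is b = 0 and a single test returns to 5%. The sample size does not change.

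**The case against.** The strongest reply is that this is a gap in reporting, not evidence of biased reading. Much of that stands, and it rules out several stronger readings that a reader might infer.

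- *Hand-drawn regions decide effectiveness.* The document names no primary endpoint. Imaging shares the effectiveness assessment with functional testing, and ROI is one of four DTI entries in Table 1, beside TBSS.
- *The image readers know the arm.* Nothing says so. Section 8 gives that knowledge to the study coordinator, and Section 15 has the data analysed under codes with identifiers filed separately. It is also unsettled whether arm follows team: the Abstract has athletes randomly assigned, while Section 6 refers to participants or school teams.
- *Regions are drawn afresh at each visit, adding noise to the change.* This is plausible, because normalisation is mentioned afterwards, but the text does not say whether drawing is per scan or in which image space.
- *The error rates describe this trial.* They do not, because the shifts are assumed. The 75-per-arm case takes the maximum recruitment with no loss, and if athletes are clustered by team, a correctly enlarged standard error would lower the figures.
- *A reader would push in a known direction.* In unprotected athletes the hockey trial reported RD rising, while the football trial reported MD, AD and RD falling.

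What the reply does not remove is that a manual method is prescribed for a measure bearing on effectiveness, the design does not conceal allocation during the season, and no text protects the reading. TBSS is listed, but nothing ranks it above the manual regions.

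**Conclusion.** The point holds as a described risk of unknown size. The plan commits to manual regions and does not describe masking of the reader to arm or visit. It does not follow that reading will be unmasked; if readers are masked in practice, a sentence saying so would settle most of the point. That the trial is open-label is itself an inference, from a collar versus no-collar comparison with no sham.

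The between-arm contrast is exposed only to bias that differs by arm. Knowledge of visit alone mainly threatens within-arm pre/post statements. The illustration gives error rates of about 9% to 45% for arm-related shifts of 0.1 to 0.3 SD at 75 per arm, and about 8% to 32% at 50 per arm. It assumes equal arms, independent athletes, a single test and shifts of those sizes. It shows that a modest shift would matter, not that one will occur.

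**What to change.** In Section 9 (Data Analysis), do one of the following:
- define the regions once on the common template and apply them unchanged to every normalised scan; or
- give the TBSS analysis already listed in Table 1 precedence, with manual regions as supportive.

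Wherever manual drawing is kept, recode the scans and present them in random order so that the reader sees neither arm nor visit, and say so in the plan. Reporting intra- and inter-reader agreement would also address repeatability.

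The cost is plan wording and a small relabelling task, with no change to sample size or visits. Template regions bring some registration error for athletes with unusual anatomy. Any agreement exercise needs reader time, which cannot be costed here because the document does not give the number of readers.

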**(2) PURPOSE OF STUDY:**

The purpose of the study is to monitor longitudinal changes in brain structure and function between the preseason and postseason, in a population of soccer playing athletes wearing the Device and compared to a similar population not wearing the device. Secondly, the purpose

is to determine the protection of the device relative to amount and magnitude of sustained head impacts.

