D. fMRI and CO2 reactivity was performed on 12 adults before and after application of jugular vein compression. Results comparing before and after jugular vein compressions (with the collar) yielded no alterations in O2 uptake or glucose metabolism to any portion of the brain.(Fisher, Duffin et al. 2013).

E. An *in vivo* clinical trial was approved by CCHMC IRB and was completed in the Cincinnati Children's Hospital Human Performance Laboratory and Radiology Department (Study ID: 2014-5009; PI: [name]) An *in vivo* clinical trial was performed in hockey players of the proposed intervention device used during sporting competitions to test its effect in ameliorating neuroanatomical and neurophysiological changes to the brain using two widely accepted techniques [diffusion tensor imaging (DTI), and event related potentials (ERPs) utilizing electroencephalography.](Reches, Laufer et al. 2014) For athletes in the non-intervention group, radial diffusivity (RD, DTI parameter associated with white matter structural integrity(Song, Sun et al. 2003, Song, Yoshino et al. 2005)) increased significantly from pre-season to mid-season. By comparison, the athletes in the intervention group did not show a significant change in RD with similar accumulated g-force head impacts. In kind, ERP analysis showed concomitant changes in brain network dynamics in the non-intervention group—the level of change was strongly correlated with the accumulated g-force of the collisions, whereas the intervention group showed no significant change. These group differences indicate that mild jugular vein compression may provide protection from the detrimental effects of collisions and resultant brain injury. These prospective longitudinal data utilized an internal (*in vivo*) approach and demonstrate that it is possible to protect the brain from sports related head impacts.

F. An *in vivo* clinical trial was approved by CCHMC IRB and was completed in the Cincinnati Children's Hospital Human Performance Laboratory and Radiology Department (Study ID: 2015-2205; PI: [name]) The *in vivo* clinical trial was performed in football players implementing the proposed intervention device used during sporting competitions to test its effect in ameliorating neuroanatomical changes to the brain using evidenced by

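### Effectiveness rests on many imaging and functional tests, each at two-sided .05, with no primary measure, no multiplicity control and no rule for which results establish it

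*Combined protocol and SAP*

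**What the plan says.** The Abstract sets the basis for judging the device: "Effectiveness of the device will be determined via differences in longitudinal brain imaging and functional testing following competitive soccer participation". Section (2) gives a broad order of aims. It begins "The purpose of the study is to monitor longitudinal changes in brain structure and function between the preseason and postseason", comparing device wearers with non-wearers, and puts protection relative to head impacts second.

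Section (9), Data Analysis, lists four DTI measures (FA, MD, AD, RD). It gives three white-matter areas as examples of regions of interest: corpus callosum, internal capsule and external capsule. Voxel-based comparison, fibre tracking and resting-state connectivity are added. Table 1 in section (4) lists the DTI analysis as "Visual/ROI/TBSS/structural connectivity".

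Statistical considerations fixes the level: "Unless otherwise stated, statistical tests are considered two-sided and a .05 significance level is used". Nothing later in section (9) sets another level for an outcome comparison; the .10 threshold there governs only whether nonlinear terms are dropped. The same paragraph proposes wide use of 95% confidence intervals to quantify efficacy.

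Statistical analyses applies ANCOVA to collar versus no collar without singling out an outcome, and labels only the Poisson rate comparison secondary. Reaction time has its own ANOVA, and each oculomotor variable has a separate one.

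**The concern.** When several outcomes can each support a claim of effectiveness and each is tested at .05, the chance that at least one is significant under no effect exceeds .05. Without a primary measure or a success rule, the reader cannot tell which result the trial was designed to deliver, and the choice can be made after the data are seen. The confidence intervals do not help: an unadjusted 95% interval excludes zero exactly when the matching .05 test rejects.

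At stake is how a positive report is read. A significant collar difference in one DTI measure in one region could be a device effect or the most favourable of many null comparisons, and the plan gives no prior statement to separate the two.

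**Working it through.** The plan states no familywise error rate, power or derived sample size, so there is no figure of its own to reproduce. Everything below is illustrative.

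**Inputs from the documents.** Two-sided .05 per test (critical |z| = 1.96); four DTI measures; three example regions; at most 150 participants (section (6)).

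**Assumed.** All correlations; the count 4 × 3 = 12; the decision rules; an effect of 0.5 SD; equal arms of 150/2 = 75 with no loss.

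**Reference case.** With 12 independent tests, P(at least one) = 1 − .95^12 = .460. The DTI measures cannot be independent, because MD = (AD + 2·RD)/3.

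**Simulation.** 400,000 null draws per setting, MD built from AD and RD, the same correlation between every pair of regions:

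- FA–AD −.7, FA–RD −.9, AD–RD .9, between-region .95: at least one 13%, at least two 10%.
- FA–AD .3, FA–RD −.7, AD–RD .3, between-region 0 / .5 / .95: at least one 35% / 31% / 19%, at least two 17% / 16% / 14%.
- FA, AD and RD mutually uncorrelated, between-region 0: at least one 40%, at least two 15%.

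**Cross-check.** With one common correlation for all pairs of the 12 tests, numerical integration gives P(at least one) = 39.7% at .3, 31.9% at .5, 18.6% at .8, 13.5% at .9 and 10.5% at .95. So 13% to 40% is a range over plausible settings, not a pair of bounds.

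**Both-required rule.** If success needs an imaging result and a functional result, the joint false-positive probability cannot exceed the smaller of the two separate ones. It is therefore lower than the any-one imaging figure.

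**Effect of control.** .05/12 = .00417 per test. Familywise error is 1 − (1 − .00417)^12 = 4.9% under independence, 3.8% at common correlation .5 and 2.2% at .8.

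**Power.** Two-sample t-test, noncentrality 0.5 × √(75/2) = 3.06, 148 df: .860 at .05 and .561 at .00417, the level of Holm's first step.

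**Unit of allocation.** These figures assume independent participants. If teams were allocated and permuted, the smallest two-sided p with three teams per arm is 2/C(6,3) = 2/20 = .10.

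**The case against.** The strongest reply is that the inflated figure belongs to a rule that the plan never states. This stands. The Abstract's wording can be read as requiring both imaging and functional differences, and nothing says that one significant region would suffice. The 12-test family is also a construction: the regions are examples, Table 1 includes TBSS, and voxel-based analysis is described as something that can be done to explore. A reader might infer that the trial has a false-positive rate of a third or more; the documents do not support that.

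A second reply is that the work is partly descriptive, since section (2) speaks of monitoring change. This stands only in part, because the Abstract speaks of determining effectiveness and section (9) of quantifying efficacy.

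A third reply points to Summary of Prior Work, item F, which mentions primary outcome measures and corrected p-values. Both describe the completed football study, and neither is carried into this trial's analysis section.

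A reader might also infer that no positive result could be separated from selection. That goes too far: a p-value below .05/12 within the illustrative family, or full reporting of every measure and region, would allow a judgement.

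Nor do the prior studies contradict each other on direction. Item E reports that RD in hockey controls "increased significantly from pre-season to mid-season", and item F reports "Significant pre- to post-season reduction in MD, AD, and RD" in football controls. The sports and intervals differ, and direction bears on interpretation, not on the two-sided error rate.

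**Conclusion.** The concern holds as a gap in the decision rule. The plan judges effectiveness from imaging and functional differences, tests at two-sided .05, and gives no primary measure, controlled family or success criterion. The broad order of aims in section (2) and the secondary label on the Poisson analysis do not narrow the imaging and functional comparisons.

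The size is conditional. Under an any-one rule over 12 DTI tests, the error is about 2.6 to 8 times nominal (13/5 to 40/5). Under a two-of-12 rule it is about 2 to 3.4 times (10/5 to 17/5). These ratios rest on assumed correlations, an inferred family and rules that the plan does not contain. The need for a rule does not depend on the exact figure. It should be settled before analysis, because it cannot be settled credibly afterwards.

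**What to change.** Before analysis, adopt one of two options in the SAP:

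- (a) Name one primary between-arm comparison of baseline-adjusted pre-to-post change in one DTI measure, over a fixed region or the white-matter skeleton, tested at .05.
- (b) Fix the DTI measures and regions and control that family by Holm or max-statistic permutation, with familywise-corrected p-values for voxel maps.

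Place functional outcomes and impact analyses in a hierarchy or co-primary rule of the sponsor's choice, or report them without confirmatory claims. Error control does not require demoting them, and the Abstract and section (2) give them standing.

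Either option holds 5% only if the analysis uses the unit actually allocated. The Abstract says "Athletes participating in this study will be randomly assigned to one of two groups", section (6) refers to participants or school teams, and Injury Surveillance in section (8) has the intervention supplied to teams by assignment. These must be reconciled. If few teams are allocated, permutation at team level may be unable to reach .05, as the .10 minimum at three per arm shows.

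The cost is SAP wording and fewer claimable results. Under the assumptions above, power is 86% with one primary measure and about 56% per test at Holm's first step. Option (a) keeps more power but could miss an effect confined to other regions; option (b) keeps regional claims at that price.
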